	possibility to reduce to two capsules tid (534 mg tid / 1602 mg daily) Day 16 three capsules in the morning only (801 mg, this is the last dose		

Boehringer Ingelheim BI Trial No.: 1199.229 c03463451-08

Trial Protocol Version 4.0

Page 5 of 118 Proprietary confidential information © 2016 Boehringer Ingelheim International GmbH or one or more of its affiliated companies

h			
Name of company:			
Boehringer Ingelheim	1		
Name of finished product:	:		
Ofev®			
Name of active ingredient	:		
Nintedanib			
Protocol date:	Trial number:		Revision date:
17 July 2015	1199.229		29 July 2016
	in the PK period)		
Mode of administration:	Ande of administration: Oral administration with food		
Duration of treatment:	16 days		
Endpoints	Pharmacokinetic Parameters:		
	Group 1:		
	Primary endpoints: AUC _{0-tz} and C _{max} of nintedanib		
	Secondary endpoin	ts: $AUC_{0-\infty}$ of nintedanib	
	Group 2:		
	Primary endpoints.	AUC and Cmar as of nirfenid	one
	1 mary enupoints. $100_{\tau,ss}$ and $C_{max,ss}$ of phreindone		
Safety criteria:	Incidence and intensity of adverse events, physical examination, vital		
	signs, ECG, change from baseline in laboratory parameters		
Statistical methods:	Descriptive statistics and analysis of variance (ANOVA) for AUC _{0-tz} ,		
	C_{max} and AUC _{0-∞} of nintedanib with and without the association with		
	pirfenidone (group	1) and for AUC _{τ,ss} and C _{max,ss} if	for pirfenidone with
	and without the ass	ociation with nintedanib (grou	p 2).

Page 6 of 118

63451-08Trial Protocol Version 4.0Page 6 ofProprietary confidential information © 2016 Boehringer Ingelheim International GmbH or one or more of its affiliated companies

FLOW CHART - GROUP 1

Trial Periods	Screening Period ¹	PK e	valuation	n Period ¹⁰	PK Follow-up Period ¹⁸
Visit	1	2	Phone call ⁶	3 ¹³	4
Weeks		0	2	311	7
Days	-28 to -1	1-2	15	23-24	52
Time window for visits			+	6 days	+3 days
Informed consent ²	Х				
Demographics	Х				
Medical history	Х				
Review of in-/exclusion criteria	Х	Х			
Drug and alcohol testing at site	Х	Х			
Physical examination	Х	Х		Х	Х
Vital signs ³	Х	Х		Х	Х
Laboratory tests	X			Х	Х
Pregnancy test (urine) ⁹	Х	Х		Х	Х
PK sample ⁷		X^{17}		X^{17}	
		Х			
		X ¹⁴		X^{14}	Х
		X^{14}		X^{14}	
12 lead-Electrocardiogram (ECG)	X				Х
Spirometry ¹²	X	Х		Х	Х
DLCO ¹⁹	X	$(X)^{19}$			
Register screening / start of treatment	X	Х			
Dispense trial drugs ⁴		X ¹⁷		Х	
Collect trial drug & compliance check				Х	
Dispense and/or collect & review diary ⁵		X^{17}		Х	

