- 4. Patient will be dispensed two wallets of pirfenidone at Visit 2 and take the full dose (801 mg tid) for 7 consecutive days (Day 1 to Day 7) and then return to the clinic for Visit 3a (Day 8). At Visit 3a they will be dispensed one wallet of pirfenidone and one bottle of nintedanib and be given the remaining wallet of pirfenidone that was dispensed at the previous visit. The will take nintedanib 150mg bid and pirfenidone 801mg tid (or 534mg tid) from Day 9 to Day 15 and then come in to the clinic at Day 16 where they will receive only the morning dose of each drug. (See Section 4.1.4).
- 5. Patients will be supplied with a diary and a dosing card and they will be asked to document the number of capsules they have taken each day and also to record any adverse events during this period.
- 6. Please see separate PK flowchart Group 2 for details during the PK evaluation period Section 10.2.
- 7.
- 8. Urine dipstick pregnancy tests will be provided by central lab and should be performed in all women of childbearing potential.
- 9. If a patient withdraws from the PK evaluation period then the patient should be managed according to Figure 4.1.4:1.
- 10. The patient will stop all trial medication on Day 16 (except for the doses given at clinic) and have a washout period from study drug until the PK FU visit.
- 11. Spirometry should be conducted using local standard equipment.
- 12. During the PK evaluation period the patient must have seven consecutive days of both nintedanib 150mg bid and pirfenidone 801mg tid (or 534mg tid) before they should have the PK day on Visit 3b.
- 13.
- 14. At Visit 4 (PK FU) optional nintedanib Named Patient Programme will be discussed with the patient
- 15. AEs and concomitant therapy should be checked at regular intervals during the PK days.
- 16. The PK Follow Up visit should occur at least 28 days after last drug intake.
- 17. DLCO testing will be performed once at visit 1 or 2, or during the screening period (visit 1 to visit 2). The results will be corrected for haemoglobin by the site, see section 10.3 for further details..

Page 10 of 118

Proprietary confidential information © 2016 Boehringer Ingelheim International GmbH or one or more of its affiliated companies

TABLE OF CONTENTS

CLINICA	L TRIAL PROTOCOL	1
TITLE PA	GE	1
CLINICA	L TRIAL PROTOCOL SYNOPSIS	2
FLOW CH	IART - GROUP 1	6
FOOTNO	ГЕS – GROUP 1	7
FLOW CH	IART - GROUP 2	8
FOOTNO	ΓΕS – GROUP 2	9
TABLE O	F CONTENTS1	0
ABBREVI	ATIONS1	4
1.	INTRODUCTION1	6

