4.1 TREATMENTS TO BE ADMINISTERED

4.1.1 Identity of BI investigational product(s) and comparator product(s)

Table 4.1.1: 1 Nintedanib (investigational drug)

Substance:	Nintedanib
Pharmaceutical formulation:	Soft gelatine capsule
Source:	BI Pharma GmBH & Co. KG
Unit Strength:	150 mg
Posology:	Group 1: Day 1 and Day 23: one 150 mg capsule in the morning
	Group 2: Days 9-15: one 150 mg capsule in the morning and one in the evening
	Day 16: one 150 mg capsule in the morning
Route of administration:	Oral (swallowed) administration with food

Table 4.1.1: 2 Pirfenidone (investigational drug)

Substance:	Pirfenidone
Pharmaceutical formulation:	Capsule
Source:	Roche Registration Limited (previously InterMune
	UK Ltd)
Unit Strength:	267 mg
Posology:	Group 1 Days 2-8: one capsule three times a day Days 9-15: two capsules three times a day Days 16-23: three capsules three times a day
	Group 2 Days 1-15: three capsules three times a day Day 16: three capsules in the morning only
Route of administration:	Oral (swallowed) administration with food

sion 4.0 Page 33 of 118

Proprietary confidential information © 2016 Boehringer Ingelheim International GmbH or one or more of its affiliated companies

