3b	0	

Group 2

The patient will come to the clinic for Visit 2 (this is not a PK day). They should take their full dose of commercial supply of pirfenidone the previous day and then stop taking their commercial supply. At the clinic, eligible patients will receive two wallets of pirfenidone. The patient will take the first dose at the clinic in the morning with food and a glass of water, under supervision and then go home and continue dosing at home. A dosing card will be provided to the patient which will explain how they should take their study medication during the trial.

Once the patient has had 7 consecutive, stable days on 801 mg tid (3 capsules 3 times a day; this can be reduced to 534 mg tid) they would then come to the clinic for the next PK visit (Visit 3a, Day 8; see flowchart and section 10.2; there is a 3 day window to ensure that the patient has 7 consecutive days at full dose).

The patient will return to the clinic for Visit 3a. They should not take their medication at home, but should bring it to the clinic with them. At the clinic, they will be given their morning dose of 801mg pirfenidone (or 534mg if they have dose reduced) at the clinic with food and a glass of water. They will also be given their second dose of pirfenidone at the clinic at 14:00. They will take their final dose of pirfenidone at 20:00 in the evening at home once they have left the clinic. They should be advised to take this with food and a glass of water. Before they leave the clinic they will be given another wallet of pirfenidone and a bottle of nintedanib to take home (they should also be given the remaining pirfenidone wallet from the previous visit once compliance has been assessed). They will be advised to start the nintedanib with the morning and evening doses of pirfenidone.

For the next 7 days the patient will continue on pirfenidone 801 mg tid (3 capsules 3 times a day; or 534 mg tid) and take nintedanib 150 mg twice a day. Once the patient has had 7 consecutive stable days on 801 mg (or 534 mg) pirfenidone tid and nintedanib 150 mg twice a day then they would come to the clinic for the next PK day (Visit 3b, Day 16; there is a three day window for this visit to allow for 7 consecutive days if required; see Figure 3.1:1).

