The patient will return to the clinic for Visit 3b. They should not take their medication at home, but should bring it to the clinic with them. At the clinic, they will be given their morning dose of 801mg pirfenidone and they will also receive one 150 mg capsule of nintedanib at the clinic with

food and a glass of water. The patient will then have a washout of 28 days where no study medication is taken and then they will return to clinic for the PK Follow-Up visit (see Flowchart).

If the patient does not achieve 7 consecutive, stable days prior to visit 3b plus the 3 day window then the patient would stop medication and attend the clinic for Visit 3b, but would not have the PK samples taken (See Figure 4.1.4:1).

Group 1 patients

Figure 4.1.4: 1 Guidance for patients who withdraw or do not tolerate uptitration during the PK evaluation period
Page 37 of 118

Proprietary confidential information © 2016 Boehringer Ingelheim International GmbH or one or more of its affiliated companies

Group 2 patients Day 1-7

Patient can start at either point

Figure 4.1.4:1 Guidance for patients who withdraw or do not tolerate uptitration during the PK evaluation period continued

Page 38 of 118

Proprietary confidential information © 2016 Boehringer Ingelheim International GmbH or one or more of its affiliated companies

Group 2 patients Day 9-15

Patient can start at either point

Figure 4.1.4:1 Guidance for patients who withdraw or do not tolerate uptitration during the PK evaluation period continued

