4.1.4.1 Nintedanib and pirfenidone

The Investigator should emphasise to the patient the importance of taking all doses of trial medication in order to avoid missed doses throughout the PK period.

Group 1

- If a dose of pirfenidone is missed, administration should resume at the next scheduled time at the recommended dose. Double doses should not be taken to make up for the forgotten capsules.
- It is recommended that pirfenidone is administered at the same time in the morning and evening with food and a glass of water, with the third pirfenidone dose administered at the midpoint with food and a glass of water.

• If a patient withdraws from the PK period or is unable to tolerate uptitration please refer to Figure 4.1.4:1.

Group 2

- The patient should swallow nintedanib unchewed with food and a glass of water twice daily and should observe a dosing interval of approximately 12 hours.
- If a dose of pirfenidone or nintedanib is missed, administration should resume at the next scheduled time at the recommended dose. Double doses should not be taken to make up for forgotten capsules.
- It is recommended that nintedanib and pirfenidone are administered together at the same time in the morning and evening with food and a glass of water, with the third pirfenidone dose administered at the midpoint with food and a glass of water.
- If a patient withdraws from the PK period or is unable to tolerate uptitration please refer to Figure 4.1.4:1.

Patients experiencing adverse events may require drug interruption or reduction of dose. For additional details refer to section 4.2.1.

2403 mg daily (801 mg tid) pirfenidone may be reduced to 1602 mg daily (534 mg tid) to manage adverse events (in Group 2 only). If dose reduction is required for pirfenidone then the patient must have 7 stable days at the reduced dose along with the nintedanib for the second PK day. Further dose reductions for pirfenidone are not permitted within the trial. If the patient has tolerability issues they should contact the Investigator immediately.

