The PK evaluation period for this group is for a minimum of 16 days plus 28 days follow-up and begins at Visit 2.

Visit 2 Day 1

- Review concomitant therapy and any adverse events since screening.
- A drug and alcohol test will be done at the clinic.
- Physical examination and vital signs.
- Urine pregnancy test for women of childbearing potential.
- Spirometry
- Reassessment of inclusion/exclusion criteria.
- •
- Registration of treatment start by emailing the form provided in the ISF to the sponsor.
- No PK samples are taken on this day.
- Dispense two wallets of pirfenidone and instruct the patient to take 801mg tid, the first dose should be given at the clinic with food and a glass of water.
- Provide patient with dosing instructions.
- Dispense diary.
- Remind patient of Visit 3a scheduled for Day 8.

Visit 3a Day 8

Once the patient has been on stable, full dose pirfenidone for 7 days (a 3 day window is allowed to ensure 7 consecutive days) they will return to clinic for the first PK day.

The patient should attend the clinic at approximately 07:00 so that the following assessments can be started before breakfast is given:

- Physical examination and vital signs.
- Urine pregnancy test for women of childbearing potential.
- Blood sample for laboratory tests (Section 5.3.3)

- Pre-dose PK samples should be taken according to PK Flowchart (Group 2, this should be taken prior to the other blood samples).

•

- Spirometry.
- Review concomitant therapy and any adverse events since previous visit and throughout the day at regular intervals.
- Patients will return all unused medication. Medication compliance will be assessed by counting returned (unused) capsules.
- The patient will return the diary card and this will be reviewed to check that the patient has received seven consecutive, stable days of treatment.
- Three 267 mg pirfenidone capsules should be given to the patient at 08:00 during breakfast (See PK Flowchart Group 2).
- PK samples should be taken according to PK Flowchart (Group 2).
- The patient should be given lunch at 12:00.
- Three 267 mg pirfenidone capsules will be given to the patient at 14:00 with a snack.
- After the PK time point at 14:00, the patient can leave the clinic.
- The patient should be given the remaining pirfenidone from the previous visit and also one new wallet of pirfenidone and one bottle of nintedanib to take home.

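### Group 2: the protocol is inconsistent about the pirfenidone dose a reduced patient takes on the two PK mornings, and no visible rule handles a pair of profiles taken at unequal doses

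*Protocol*

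**What the plan says.** **Reduction is allowed.** The synopsis permits two capsules tid anywhere in Days 1 to 15. Protocol 4.1.4 allows 534 mg tid in the run-in to either PK visit. Section 4.2.1.1 allows it in Group 2 without naming a start day, and the footnote to 4.2.1 foresees dose reduction before Visit 3a as well as Visit 3b. Footnote 12 of the Group 2 flow chart says of the run-in to Visit 3b that "the patient must have seven consecutive days of both nintedanib 150mg bid and pirfenidone 801mg tid (or 534mg tid". Section 4.1.4.1 adds that after a reduction "the patient must have 7 stable days at the reduced dose along with the nintedanib for the second PK day".

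**Visit 3a (Day 8, reference).** Section 4.1.4 says "they will be given their morning dose of 801mg pirfenidone (or 534mg if they have dose reduced". Section 6.2.2 gives three 267 mg capsules with no reduced option, for a patient it describes thus: "Once the patient has been on stable, full dose pirfenidone for 7 days". Flow chart footnote 4 likewise has patients "take the full dose (801 mg tid) for 7 consecutive days (Day 1 to Day 7".

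**Visit 3b (Day 16, test).** Table 4.1.1:2 has "Day 16: three capsules in the morning only". Section 4.1.4 says "they will be given their morning dose of 801mg pirfenidone and they will also receive one 150 mg capsule of nintedanib". The synopsis and 6.2.2 also give 801 mg. None of the four offers 534 mg.

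**Analysis.** The ANOVA (Protocol 7.3.1, SAP 9.1) has subject and treatment effects only. The dose-related exclusion example in Protocol 7.3 concerns doses that depart from the protocol. SAP Table 6.2:1 has no row for unequal doses, and its incorrect-medication row (C1) excludes nobody from the PK analysis set. SAP 5.4.2 uses dose reductions only to describe exposure.

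**The concern.** The Group 2 primary ratio compares each patient's pirfenidone exposure with and without nintedanib. It isolates nintedanib only if the pirfenidone dose and run-in are the same on both mornings. For a reduced patient the text does not secure this. A site following 4.1.4 exactly gives a patient reduced before Day 8 a 534 mg reference and an 801 mg test, with no deviation to record. The excess exposure then enters the ratio as if nintedanib had caused it.

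Two further consequences follow from the Day 16 text. The endpoints are AUCτ,ss and Cmax,ss, but 801 mg after a week at 534 mg tid is not a steady-state profile. And a patient reduced for adverse events takes a full dose again while on nintedanib.

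**Working it through.** **1. The plan's own precision figure.** Table 7.7:2, first row: N = 12, total gCV 30%, correlation 0.5.

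- Within-subject variance = ln(1 + 0.30²) × (1 - 0.5) = 0.0431, so the intra-individual gCV is 21.0% (stated 21).
- Half-width on the log scale = t(0.95, 11) × √(2 × 0.0431/12) × √(χ²(0.95, 11)/11) = 1.796 × 0.0847 × 1.337 = 0.2035.
- 90% CI = 81.6 to 122.6% (stated 82 to 123). The other CIs in that table also reproduce after rounding.

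**2. Dose-only ratios.** Inputs: half-life 3 h and fed tmax 3 h (Protocol 1.2.2); doses at 08:00, 14:00 and 20:00; AUC over 0 to 6 h; Cmax at the scheduled sampling times (Protocol 10.2). Assumptions: one compartment, dose proportionality, no interaction, 7 days of run-in. These give ke = ln 2/3 = 0.231/h and ka = 0.462/h.

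Superposition puts the share of the steady-state AUC that comes from earlier doses at f = 0.175. Then:

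- 801 mg after a 534 mg run-in, relative to 801 mg steady state: 1 - f/3 = 0.942 (Cmax 0.954).
- 801 mg after a 534 mg run-in, relative to 534 mg steady state: 1.5 - f/2 = 1.412 (Cmax 1.431).
- 534 mg steady state relative to 801 mg steady state: 534/801 = 0.667.

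| Patient | Visit 3a dose (source) | Visit 3b dose (source) | T/R, AUC |
|---|---|---|---|
| Reduced before Day 8 | 534 mg (4.1.4) | 801 mg (4.1.4) | 1.41 |
| Reduced before Day 8 | 801 mg (6.2.2) | 801 mg (6.2.2) | 1.00 |
| Reduced before Day 8 | 801 mg (6.2.2) | 534 mg (4.1.4.1, inferred) | 1/1.412 = 0.71 |
| Reduced before Day 8 | 534 mg (4.1.4) | 534 mg (4.1.4.1, inferred) | 1.00 |
| Reduced after Day 8 | 801 mg | 801 mg (all stated amounts) | 0.94 |
| Reduced after Day 8 | 801 mg | 534 mg (4.1.4.1, inferred) | 0.67 |

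Over half-lives of 2 to 4 h and tmax of 0.5 to 3 h, the 1.41 runs from 1.37 to 1.49 and the 0.94 from 0.92 to 0.99 (AUC and Cmax).

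**3. Effect on the pooled ratio.** With k such patients among 12, the GMR is multiplied by r^(k/12).

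| r | k = 1 | k = 2 |
|---|---|---|
| 1.412 | 1.029 | 1.059 |
| 0.942 | 0.995 | 0.990 |
| 0.708 | 0.972 | 0.944 |
| 0.667 | 0.967 | 0.935 |

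**4. Effect on the CI width.** One such patient multiplies the log-scale width by √(1 + (ln r)²/(12 × s²)), with s² = 2 × ln(1 + 0.21²) = 0.0863. This is 1.056 for r = 1.412, 1.076 for r = 0.667 and 1.002 for r = 0.942.

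**The case against.** The strongest reply is that every stated Day 16 amount is 801 mg. Section 4.1.4.1 sets a run-in condition and names no dose for the PK morning. On the stated amounts, a patient reduced after Day 8 gets 801 mg twice, and the GMR moves by only about 0.5% per patient in 12. A 534 mg dose on Day 16 would then arguably be too low and fall under the Protocol 7.3 example. This stands: 0.67 and 0.71 need an inferred reading.

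It does not answer the patient reduced before Day 8. There 4.1.4 and 6.2.2 conflict openly at Visit 3a, and following 4.1.4 at both visits gives 1.41 with no non-compliance for 7.3 to catch.

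A reader might infer that one patient's ratio can run from 0.67 to 1.41 according to the section the site follows. The documents do not support that: 0.67 needs reduction after Day 8 and 1.41 needs reduction before it.

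A reader might also infer that the plan has no means of handling such pairs. That is too strong. The 7.3 criteria are examples, and SAP Table 6.2:1 may be supplemented by the report planning or database lock meeting. Its row E4 can exclude patients for procedural violations, though a permitted reduction is not a violation. Figure 4.1.4:1, the further-endpoint sections and the sponsor's PK procedures could not be checked.

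Finally, the trial is exploratory and Group 2 entry requires full-dose pirfenidone, so reduced patients may be few or none. This limits the size of the problem but does not settle the dose.

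**Conclusion.** The point holds. The PK-morning dose for a reduced Group 2 patient is inconsistent at Visit 3a. At Visit 3b it is out of step with the reduced run-in. No visible text says how a permitted unequal-dose pair enters the primary ratio.

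The size is modest: per affected patient in 12, about +3% on the GMR (1.41), about -3% under the inferred readings (0.67 to 0.71), or -0.5% (0.94), against a planned 90% CI of about 82 to 123%. These figures assume dose proportionality, one-compartment kinetics and no true interaction. The number of affected patients is not given and may be zero. The correction is worth making because the shift has nothing to do with nintedanib, its direction depends on which section a site follows, and the remedy is cheap.

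**What to change.** **Dosing text.** In the synopsis, Table 4.1.1:2, 4.1.4 and 6.2.2, give the current run-in dose on both PK mornings: 801 mg, or 534 mg if reduced.

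**Analysis text.** In Protocol 7.3 and SAP 6.2, state that pairs taken at unequal pirfenidone doses do not enter the primary ratio un-normalised. Choose one approach as primary and report the other as sensitivity:

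- dose-normalise AUC and Cmax, stating the proportionality assumption; or
- flag both profiles of the pair for exclusion (KPEXC, SAP 7.4) and leave the pair out of the 12 evaluable patients.

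Both profiles must be flagged because 7.3 keeps a patient with a single value. One 534 mg test value left beside 11 complete pairs has weight 0.0417 in the random-subject model at correlation 0.5, so it still moves the GMR by 0.0417 × ln 1.5 = 1.7%. Keep 534/534 pairs.

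**Cost.** A protocol text correction and a short SAP entry, with no new procedures. With run-in doses on both mornings, every patient reduced after Day 8 becomes an 801/534 pair, so the choice matters. Normalising keeps these patients but rests on proportionality. Excluding them removes the less tolerant patients and uses the allowance of 6 dropouts in 18. An excluded pair that is not replaced widens the log-scale CI by 5.4%: t(0.95, N-1)/√N goes from 0.5184 at N = 12 to 0.5465 at N = 11. The top-up provision in Protocol 7.7 can replace it.

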4.1.5 Blinding and procedures for unblinding

4.1.5.1 Blinding

In this open-label trial, treatment allocation will not be concealed throughout the trial. The CRF will contain information on the group to which a patient has been allocated.

4.1.5.2 Unblinding and breaking the code

Not applicable. This is an open label trial.

4.1.6 Packaging, labelling, and re-supply

The medication kit for nintedanib is a 75cc PE bottle and contains 30 capsules. These will be provided by BI.

Medication kits for pirfenidone will comprise of a blister package of 63 capsules in a blister package (wallet). These will be provided by BI.

For details of packaging and the description of the label, refer to the ISF.

Medication will be provided by the Department of Pharmaceutical Development of Boehringer Ingelheim Pharma GmbH & Co. KG, Biberach, Germany.

No re-supply is planned.

The nintedanib used in the nintedanib Named Patient Programme does not form part of the study supplies.

